6.3 Concomitant medications

The patient must be told to notify the investigational site about any new medications he/she takes after the start of the study drug. All medications (other than study drug) and significant non-drug therapies (including physical therapy, herbal/natural medications and blood transfusions) administered during the study, and those taken 30 days prior to study entry must be listed on the Concomitant Medications CRF.

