7.3.1.2 Supportive care

The need for platelets and red cells transfusions will be monitored at each visit as noted in [Table 7-1](#).

The concomitant use of G-CSF and/or EPO therapy will be recorded at each visit, as outlined in [Table 7-1](#).

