10.5.1 Other efficacy objective(s)

- To determine the response in each haematological lineage separately, the absolute frequency and valid percentage of patients who have a response in the neutrophil, platelet, and Hb lineages separately after 16, 24 and 36 weeks of eltrombopag, will be presented with the 95% CI. Descriptive statistics will also be provided between baseline and weeks 16, 24 and 36 for ANC, platelets and hemoglobin levels, and the appropriate paired exploratory tests will be done according to the type of distribution (parametric or not) to assess the statistical significance of the changes.
- To evaluate the overall hematological response rate (partial and complete) at 24 and 36 weeks after the initiation of eltrombopag, the frequency and percentage distribution and the corresponding 95% CI will be provided. This CI will be constructed as for the primary efficacy endpoint. Descriptive statistics will also be provided between baseline and week 24 and week 36 for ANC, platelets count and hemoglobin levels, and the appropriate paired exploratory tests will be done according to the type of distribution (parametric or not) to assess the statistical significance of the changes.
- To evaluate transfusion independence, the percentage of patients who were previously transfusion-dependent and do no longer require a RBC or platelet transfusion before and after the first 16 weeks of treatment will be calculated along with the 95% CI. This CI will be constructed as for the primary efficacy endpoint. The period where patients did not receive any platelet or RBC transfusions during the treatment period and follow-up will also be analyzed.

- To evaluate the discontinuation or reduction of concomitant G-CSF and/or EPO therapy, the percentage of patients who discontinue or reduce by $\geq 50\%$ from baseline the use of concomitant G-CSF and/or EPO therapy will be calculated along with the 95% CI. This CI will be constructed as for the primary efficacy endpoint.
- Overall survival, defined as the duration from inclusion in the study to date of death (whatever the cause), will be estimated with the Kaplan-Meier curves method and two-sided 95% CI for the estimated median. All patients who discontinue from the study, regardless the reason of discontinuation, will be followed for survival for 24 and 36 weeks, unless they withdraw their consent, die or are lost-to follow-up, in which case will be censored at the last contact.

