#### **10.5 Secondary objective 4**

##### **To evaluate the reduction and discontinuation of concomitant granulocyte colony-stimulating factor (G-CSF) and/or erythropoietin (EPO) therapy.**

It will be calculated:

- The patient receive EPO at start of treatment (No / Yes) (data in section "Supportive Care Record").
- The patient receive EPO in visit 6, visit 9, visit 11, visit 13, visit 15 and visit 16 (No / Yes) (data in section "Supportive Care Record").
- The patient reduce EPO at least 50% from start of treatment to visit 6, visit 9, visit 11, visit 13, visit 15 and visit 16 (No/ Yes) (data in section "Supportive Care Record").
- The patient receive G-CSF at start of treatment (No / Yes) (data in section "Supportive Care Record").
- The patient receive G-CSF in visit 6, visit 9, visit 11, visit 13, visit 15 and visit 16 (No / Yes) (data in section "Supportive Care Record").
- The patient reduce G-CSF at least 50% from start of treatment to visit 6, visit 9, visit 11, visit 13, visit 15 and visit 16 (No / Yes) (data in section "Supportive Care Record").

It will be realized:

- Analysis of contingency tables between number of patients who receive EPO at start of treatment and in visit 6, visit 9, visit 11, visit 13, visit 15 and visit 16, using chi-square or Fisher's exact test.
- Analysis of contingency tables between number of patients who receive G-CSF at start of treatment and in visit 6, visit 9, visit 11, visit 13, visit 15 and visit 16, using chi-square or Fisher's exact test.

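### SAP 10.5 reads G-CSF and EPO use at six selected visits against one reading at start, so a starting user who is between courses can be flagged as stopped or reduced without any true change

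*SAP*

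**What the plan says.** Protocol 10.5.1 asks for the percentage of patients who stop, or cut by at least half, "from baseline the use of concomitant G-CSF and/or EPO therapy will be calculated along with the 95% CI". Neither there nor in Table 3-1 does the protocol give a time point, a look-back period, a unit for the halving or a requirement that a stop should last.

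SAP 10.5 puts this into practice with visit flags. The reference is a single reading: "The patient receive G-CSF at start of treatment (No / Yes"). Follow-up is read at six visits: "The patient receive G-CSF in visit 6, visit 9, visit 11, visit 13, visit 15 and visit 16 (No / Yes"), and likewise "The patient receive EPO in visit 6, visit 9, visit 11, visit 13, visit 15 and visit 16 (No / Yes"). Halving is a yes/no flag over the same visits, beginning "The patient reduce G-CSF at least 50% from start of treatment to visit 6". Contingency tables then compare the numbers receiving each agent at start and at each listed visit.

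On data collection, Protocol 7.3.1.2 states: "The concomitant use of G-CSF and/or EPO therapy will be recorded at each visit". Protocol 6.3 requires all medications given during the study, "and those taken 30 days prior to study entry must be listed on the Concomitant Medications CRF". Protocol 6.3.1.1 permits both agents without fixing a schedule.

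SAP 10.4, the section just before, handles transfusions differently. It counts them over intervals (before start, start to week 16, week 16 to end of treatment) and cites the same Supportive Care Record.

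**The concern.** The endpoint is a change in the use of a supportive drug. The plan reads it at isolated points. If use comes in courses, choosing patients who are on the agent at one point and looking once later produces an apparent fall even when nothing has changed, which is regression to the mean. Because the endpoint counts only falls, a starting user with unchanged use can be misread in one direction only.

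This matters because the hematologic response definitions (Protocol 7.3.1.1) require transfusion independence for platelet and hemoglobin partial responses, but set no condition on G-CSF for the neutrophil response. Objective 4 is therefore the visible planned efficacy analysis that would show whether neutrophil recovery came with less growth-factor support. The trial has one arm, so no comparator would expose a spurious reduction.

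**Working it through.** The documents give no expected rate, user count or power for this endpoint, so there is no plan figure to reproduce. The check maps the visits, then sizes the possible error under stated assumptions.

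**1. Visits used.** From Protocol Figure 4-1: visit 6 = week 4, 9 = week 10, 11 = week 16, 13 = week 24, 15 = week 36, 16 = week 40. Visits 3 to 16 follow Day 1, which makes 14. SAP 10.5 uses 6 and leaves out 8 (weeks 1, 2, 3, 6, 8, 12, 20 and 30).

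**2. Assumptions (not in the documents).** A patient is on the agent in a fraction q of weeks, with q constant throughout, so there is no treatment effect. Status follows a two-state weekly chain with week-to-week correlation ρ between 0 and 0.8. The visit record is taken as status at the visit.

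**3. One visit against one start reading.** P(off at week t, given on at Day 1) = (1 − q)(1 − ρ^t). At t = 16 and ρ = 0.8, ρ^16 = 0.028. For q = 0.5 this gives 0.5 × 0.972 = 0.486, and with ρ = 0 it gives 0.5.

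**4. No use in a 28-day window.** Take four weekly states before Day 1 and four ending at week 16, among patients with any use in the first window. Let s = 1 − q(1 − ρ), the chance of staying off from one week to the next.
- Whole window off: P(B) = (1 − q)s³, and the same for the baseline window.
- Both windows off: P(AB) = P(B) × [1 − q(1 − ρ^13)] × s³.
- False discontinuation = [P(B) − P(AB)] / [1 − P(B)].

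For q = 0.5 and ρ = 0.8: s = 0.9, P(B) = 0.5 × 0.729 = 0.3645, P(AB) = 0.3645 × 0.5275 × 0.729 = 0.140, and the result is 0.224/0.6355 = 0.353.

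| q | Off at week 16, single visit | No use in 28 days, ρ = 0 | ρ = 0.5 | ρ = 0.8 |
|---|---|---|---|---|
| 0.5 | 49–50% | 6.3% | 21.1% | 35.3% |
| 0.7 | 29–30% | 0.8% | 8.2% | 18.5% |
| 0.9 | 10% | 0.0% | 1.7% | 5.4% |

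**5. Halving.** Counting on-weeks in the same two windows and enumerating all patterns, the chance that an unchanged user shows a fall of at least 50% at ρ = 0.8 is 48% for q = 0.5 and 30% for q = 0.7. That is hardly better than the single-visit figures. Windows help discontinuation much more than they help halving.

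**6. Combining visits.** The SAP does not say how six flags become one patient result. If visits are independent (ρ = 0) and q = 0.5, an unchanged starting user is off at one given visit with probability 50%, at one or more of six with 1 − 0.5^6 = 98.4%, and at all six with 0.5^6 = 1.6%. For q = 0.9 the first two are 10% and 1 − 0.9^6 = 46.9%, and the third is close to zero. The size of the error depends heavily on a rule that is not stated.

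**7. All patients together.** Under the same model, moves from off to on, (1 − q)q(1 − ρ^t), equal moves from on to off, q(1 − q)(1 − ρ^t). The proportion of all patients receiving the agent therefore stays at q.

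**The case against.** The strongest reply is that SAP 10.5 is incomplete rather than biased. Much of this stands.

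- A reader might infer that the SAP counts patients with unchanged use as having stopped. It does not say so. It tabulates status by visit and gives no patient-level rule for discontinuation. The supportable statement is that such patients can be flagged as off or reduced.
- A reader might infer that every reading of the visit item goes wrong. That is not supported. If receiving the agent in a visit means that therapy is ongoing, an intermittent prescription would stay at yes. If the record looks back to the previous visit, most intermittent users would also stay at yes. Unequal visit intervals would distort the halving only if raw totals were compared, and the SAP does not say that they are.
- The content of the Supportive Care Record is not shown. SAP 10.4 takes interval counts of transfusions from it, so it may hold more than visit-day status.
- The whole-cohort proportions in the contingency tables do not drift under the model (step 7). The one-sided error applies to starting users, a denominator that the SAP does not state.
- The protocol sets no time point or window, so landmark visits do not contradict it.

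What remains is that the endpoint counts falls, the reference is one reading, and nothing in the SAP excludes the snapshot reading or guards against its error.

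**Conclusion.** The point holds as a weakness of definition with a possible bias, not as a demonstrated mis-scoring. SAP 10.5 compares one start reading with six selected visits and gives no look-back, persistence rule, quantity to be halved, denominator or patient-level result. On the snapshot reading, about 50%, 30% or 10% of unchanged starting users would appear off at week 16 for on-fractions of 0.5, 0.7 or 0.9. A 28-day no-use rule gives about 6–35%, 1–18% or 0–5%.

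These figures rest on intermittent use, constant q and visit-day recording, none of which the documents establish. The number of G-CSF or EPO users among the 33 planned patients is also unknown. The endpoint is secondary, and the sample size and primary analysis are untouched. The change should still be made, because otherwise the reading would be chosen after the data are seen.

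**What to change.** In SAP 10.5, for each agent separately:

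- Restrict the endpoint to patients who used the agent in the 28 days before Day 1, and report that number.
- Define discontinued as no administration in the whole 28-day window ending at week 16, 24 or 36.
- Define reduced as a mean daily dose in that window at least 50% below the mean in the 28 days before Day 1. If dose was not captured, use the number of administration days.
- Give one result per patient at each of the three time points, with its 95% CI.
- Use the records from all visits together with the Concomitant Medications CRF, and keep the visit flags as a listing.

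The baseline window should be available. Protocol 6.3 reaches back 30 days before study entry, and Table 7-1 records concomitant medication from consent onward. Dose needs checking, because the protocol does not explicitly require it for these agents.

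The cost is SAP wording and some programming, with no new visits or data collection. The reported rates will probably be less favourable. Windows do not fully remove chance halving (step 5), so the reduction result should be read with caution.

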Secondary	To determine the response in each hematological lineage separately	
- Percentage of patients who have a response in the neutrophil lineage, defined as ANC $\geq 1,000/\mu\text{L}$ or $\geq 1500/\mu\text{L}$ according with the hematological responses defined in the primary objective, confirmed in two consecutive blood tests separated a minimum of 7 days.- Percentage of patients who have a response in the platelet lineage, defined as Platelet count $\geq 20,000/\mu\text{L}$ or $\geq 100,000/\mu\text{L}$ according with the hematological responses defined in the primary objective, confirmed in two consecutive blood tests separated a minimum of 7 days.- Percentage of patients who have a response in the hemoglobin lineage, defined as Hb $\geq 100\text{ g/L}$ or $\geq 110\text{ g/L}$ according with the hematological responses defined in the primary objective, confirmed in two consecutive blood tests separated a minimum of 7 days	Refer to Section 10.5

Objective	Endpoint	Analysis
To evaluate the long-term efficacy of eltrombopag for poor graft function on overall hematologic response (partial and complete) at 24 and 36 weeks after treatment	Maintenance of hematologic response at 24 weeks and 36 weeks after the initiation of eltrombopag	
Transfusion independence: To evaluate the transfusion independence for red blood cells (RBC) and/or platelets after the initiation of eltrombopag	
- Percentage of patients previously transfusion-dependent who do no longer require platelets and/or RBC transfusion before and after the first 16 weeks of treatment.- Time period in which patients do not receive platelets and/or RBC transfusions.	
Discontinuation or reduction of concomitant G-CSF and/or EPO therapy	Percentage of patients who discontinue or reduce by $\geq 50\%$ the use of concomitant G-CSF and/or EPO therapy.	
Overall survival	Time from the date of inclusion until the date of death due to any cause. All patients who discontinue from the study, regardless the reason of discontinuation, will be followed for survival for 24 and 36 weeks, unless they withdraw their consent, die or are lost-to follow-up, in which case will be censored at the last contact.	
Overall survival rate	Percentage of patients still alive at 24 weeks and 36 weeks.	

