### **3 STATISTICAL METHODS**

Quantitative variables are described with measures of central tendency and dispersion: mean, median, SD, Q1, Q3, minimum and maximum).

Qualitative variables are described using absolute and relative frequencies (N, %). Two percentage columns are presented, total percentage (total %) and valid percentage (valid %), that is, the percentage over the sum of valid responses plus missing values and the percentage over the total of valid responses. When there are not missing values both of them are equal, and then only one will be show.

[figure not shown]
In the analysis of contingency tables as well as for the comparison of proportions and / or frequency distributions, the chi-square test (or Fisher's exact when appropriate) will be used.

For dependent samples, parametric (t-test paired) or non-parametric (Wilcoxon) statistical tests will be performed depending on the distribution of the sample.

The "time to event" variables (overall survival) will be analyzed using the Kaplan-Meier method.

These tests will be used in all bilateral cases and with a level of significance of 0.05. In cases where a p-value less than 0.05 appears, it refers to the existence of statistical significance.

Data will be analyzed using SPSS v22.0.

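### No output planned in SAP 10.5 is the protocol's single percentage of patients who stop or at least halve G-CSF and/or EPO

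*SAP*

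**What the plan says.** The protocol treats this as one endpoint. Table 3-1 lists the objective as "Discontinuation or reduction of concomitant G-CSF and/or EPO therapy" and gives it a single percentage; the protocol summary does the same. Protocol 10.5.1 says that the percentage who stop or reduce by half or more "from baseline the use of concomitant G-CSF and/or EPO therapy will be calculated along with the 95% CI", and adds: "This CI will be constructed as for the primary efficacy endpoint". Protocol 10.4.2 defines that interval as the one-sided 95% Clopper-Pearson interval.

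SAP 10.5 works agent by agent. For EPO it derives receipt at start, receipt at later visits, and "The patient reduce EPO at least 50% from start of treatment to visit 6, visit 9, visit 11, visit 13, visit 15 and visit 16". For G-CSF it derives the same set, including "The patient reduce G-CSF at least 50% from start of treatment to visit 6, visit 9, visit 11" and the remaining three visits. It then plans "Analysis of contingency tables between number of patients who receive EPO at start of treatment and in visit 6" and the five later visits, and likewise "Analysis of contingency tables between number of patients who receive G-CSF at start of treatment and in visit 6" and onward, by chi-square or Fisher's exact test. SAP section 3 covers presentation: "Qualitative variables are described using absolute and relative frequencies (N" and percentages). The opening of SAP section 10 promises 95% intervals without giving a method or a side.

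**The concern.** The SAP governs the final analysis. If it is followed as written, secondary objective 4 is reported as a grid of agent-by-visit results, and the percentage the protocol promised does not appear. No cell of the grid is marked as the answer.

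The endpoint matters for reading the rest of the trial. Protocol 6.3.1.1 permits both agents throughout, and the neutrophil and hemoglobin response criteria in Protocol 7.3.1.1 do not require independence from them. This objective is where the plan shows whether growth-factor support fell.

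**Working it through.** **1. The plan's own figure.** The documents give no figure for this endpoint. The only design figure is for the primary endpoint (Protocol 10.7): n = 33, 45% observed, one-sided 95% lower limit 30.1%. The exact lower limit is the 5th percentile of Beta(x, n − x + 1). With x = 0.45 × 33 = 14.85 it is 0.3008, a distance of 0.149, so the figure reproduces. This confirms the interval method that Protocol 10.5.1 carries over. The present point does not depend on it.

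**2. What each document produces.**

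| Item | Protocol | SAP 10.5 |
|---|---|---|
| Reduction result | one percentage, both agents | 2 agents × 6 visits = 12 percentages |
| Stopping | joined to reduction | receipt yes/no only, not joined |
| Patients on both agents | no rule | no rule |
| Denominator | not stated | not stated |
| Visit | not named | six, none designated |
| Interval | one-sided exact | 95%, method not given |
| Tests | none for this endpoint | 2 × 6 = 12 contingency tests |

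**3. Can the percentage be recovered from the agent totals?** Assume, for illustration only, 8 G-CSF users of whom 5 reduce and 6 EPO users of whom 3 reduce, at one visit. The number of distinct users is 14 minus the overlap.

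- One agent suffices, lowest: three patients use both and reduce both, so 14 − 3 = 11 users and 5 successes; 5/11 = 45%.
- One agent suffices, highest: all six EPO users also use G-CSF, and the three EPO reducers are the three who did not reduce G-CSF; 8/8 = 100%.
- Every agent must be reduced, lowest: overlap of six, nobody on both reduces both, two G-CSF-only users reduce; 2/8 = 25%.
- Every agent must be reduced, highest: the three on both reduce neither, and all five G-CSF-only and three EPO-only users reduce; 8/11 = 73%.

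The agent totals are identical in all four cases.

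**4. Effect of the rule and the denominator.** Assume 12 users at start: 5 on G-CSF only (3 reduce), 3 on EPO only (1 reduces), and 4 on both (2 reduce G-CSF only, 1 EPO only, 1 both).

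- G-CSF alone: (3 + 2 + 1)/9 = 66.7%. EPO alone: (1 + 1 + 1)/7 = 42.9%.
- At least one agent: (3 + 1 + 2 + 1 + 1)/12 = 8/12 = 66.7%, exact lower limit 39.1%.
- Every agent used: (3 + 1 + 1)/12 = 5/12 = 41.7%, lower limit 18.1%.
- Over all 33 patients: 8/33 = 24.2% and 5/33 = 15.2%.

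With these assumed data, the unstated choices move the answer from 15% to 67%.

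**5. What the tests measure.** Start and visit values come from the same patients. Suppose 8 of 33 use G-CSF at start and the same 8 still use it later. Nothing has fallen, yet the Fisher p-value is 1/C(33,8) = 1/13,884,156, about 7 × 10⁻⁸. If all 8 stop and nobody starts, the later-use column is empty and no test can be computed. If the SAP instead means a comparison of two proportions, 33 patients are treated as 2 × 33 = 66 independent observations. Either way the tests use receipt only, so a 50% reduction never enters them.

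**The case against.** Several points on the other side stand.

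- **The gaps are shared.** The protocol names no visit, no denominator and no rule for patients on both agents. A reader might infer that the SAP contradicts a settled definition of success, for instance for a patient who switches from G-CSF to EPO. It does not: the protocol has no such rule, and taken literally its wording could count that patient as a success.
- **The data are there.** Use is recorded at each visit (Protocol 7.3.1.2) and the SAP flags are patient-level, so the combined variable can be derived. The accurate statement is that it is not planned and cannot be read off the tabulated totals.
- **Agent-level tables are reasonable** as description, since the hematological lineages are also analysed separately.
- **The illustrative counts are invented**, and the ranges in step 3 are extremes of overlap. Neither document counts success at any one of the six visits, so a rate built on that rule would not describe this plan.
- **Selective reporting is not shown.** All the tables are prespecified. What can be said is that none is designated as the result.

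A reader might also infer that the protocol requires every agent to be reduced, with none newly started. Its wording does not say so, and *and/or* leaves both readings open.

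None of this supplies the missing percentage or its interval.

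**Conclusion.** The point holds in this limited form: the protocol's percentage and its exact interval are not among the SAP's planned outputs, and the planned totals do not determine them. The SAP also leaves open the visit, the denominator and the two-agent rule, which the protocol does not settle. The planned chi-square and Fisher tests do not measure reduction.

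The size of the effect cannot be estimated from the documents. The ranges in steps 3 and 4 rest on assumed counts and show only that the open choices can matter. The sample size and the primary endpoint are unaffected, and Protocol 10.8 claims no power for secondary variables. The change should be made before analysis, as an ordinary correction to a secondary endpoint.

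**What to change.** In SAP 10.5, add the combined percentage as the result for secondary objective 4, specified as follows.

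- **Denominator:** FAS patients using G-CSF and/or EPO at start of treatment.
- **Success:** stopped or reduced by at least 50% at one visit named before analysis. Visit 11 (week 16) is a suggestion: it is the primary time point, and Protocol 6.1.2 withdraws non-responders after it, so later visits describe mainly responders.
- **Missing:** patients with no assessment at that visit count as not reduced.
- **Interval:** the one-sided 95% Clopper-Pearson interval of Protocol 10.4.2.
- **Both agents:** state whether the main result needs at least one agent reduced or every agent in use at start. Report the other reading as a sensitivity result, and show new starts of the other agent alongside.

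Keep the per-agent, per-visit tables as descriptive and drop their chi-square and Fisher tests.

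The cost is SAP wording and one derived variable from data already collected. The reported rate may be slightly less favourable, for instance because patients not assessed at the named visit count as not reduced.
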